One alternative to the use of invasive temperature monitoring that may be more accurate and reliable than either chemical or electronic thermometers is the TempTraq® thermometer. This thermometer developed by Blue Spark Technologies (Westlake, Ohio) is applied to the skin as a patch. The TempTraq® thermometer is a thin, single-use, battery-powered skin patch that monitors and records skin temperature. Previous studies have demonstrated that it is reliable and accurate for monitoring temperature in children and in healthy adults. However, it has not been tested in ill adult patients.

Methods

Purpose

The purpose of this feasibility study is to assess the accuracy and precision of the Temp-Traq thermometer for monitoring body temperature in adult patients under three conditions (hypothermia, normothermia, and hyperthermia).

Specific Aims

1. To assess the accuracy of the Temp-Traq thermometer as compared to a gold standard (Core temp measured by Pulmonary Artery Catheter)
2. To assess the precision of the Temp-Traq thermometer over repeated measures
3. To determine if accuracy &/or precision is consistent in three conditions (hypothermia, normothermia, or hyperthermia)

Design

A repeated measures within-group comparative design will be used for this study.

Sample/Setting

To address the specific aims of this study we will identify patients (N = 40) who have a pulmonary artery (PA) catheter in place (patients in intensive care units). Letters of support are attached from the unit managers where the study will take place (see attached).

Inclusion Criteria

Adult patient (male or female) in intensive care unit who will have a PA catheter in place for at least the next 8 hours; and who have no visible skin condition to the axillary region upon inspection by the research nurse are eligible for this study

Exclusion Criteria

1. Patients younger than 21
2. Patients who will not have a PA catheter in place for the next 8 hours
3. Patients who have a visible skin condition to the axillary region upon inspection by

the research nurse

4. Patients who will be going for procedures or for some reason will not be available for the 6 hours of the study

Procedure

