We will use the TOST (Two One Sided t-tests) method for equivalence testing. This method requires a defined range of mean differences between two test methods, an estimate of the precision of the measurement of the two systems, and an estimate of the size of the possible difference in the means of the two methods under consideration. The TOST null hypothesis is a joint null hypothesis that the mean measurement differences between the two methods is greater than a critical lower bound and less than a critical upper bound. If the null is rejected then we can conclude that the absolute difference of the means for the two groups falls within the specified range. It was determined that to be considered equivalent with respect to accuracy the mean

measurements of the two methods should be within ± 0.2 degrees of each other. Precision tests for Temp-Traq thermometer using accepted ASTM test methods for various combinations of temperature and humidity provided a range of measurement variation between .0000435 and .019928 with a mean of 0.000254500. If we assume both test methods exhibit the same levels of precision then the variance of the differences between their two means will reduce to two times the values listed previously. This will result in estimates of the standard deviations of the mean differences of .0093, .032, and .063 respectively.

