The two methods for body temperature that will be examined are core temperature measurements with a PA catheter and temperature measurements using the Temp-Traq. Paired temperature measurements for both methods will be taken simultaneously every 2 hours for a 6 hour period. This will provide 4 repeated temperature measures per patient. The simultaneous measurements within a given patient should exhibit a high degree of correlation. If .7 is chosen as the lower bound for the correlation between the paired readings (higher correlations would result in an estimate of fewer patient samples thus the choice of .7 is conservative) and if the average standard deviation of the mean of the differences is used as an estimate of the expected variability, then it would be possible to declare measurement equivalence for a difference of $\pm .19$ with a sample size of 40 patients. This assumes the ASTM measurements of instrument variation are representative of the within patient variance. Given the vagaries of patient-to-patient this may be too optimistic an estimate. Table 1 (attached) is a summary of patient sample sizes for standard deviations equal to the average standard deviation and for 5 and 10 fold increases in this value.

A sample size of 40 patients will provide 80% or greater power for testing for equivalence between methods where the mean difference is .1 or less for up to a ten-fold increase in the estimates of the variability of the differences based on the ASTM precision measures and for a mean difference of .15 for up to a five-fold increase in these same measures. If the sample size is 40 then the power for the test of equivalence, where the difference is .15 and the standard deviation is a ten-fold increase, is 35%. Agreement testing: The Bland-Altman test will be used to test the agreement of the two methods. This test will permit a check for significance of bias between the two measures (the average difference between the two measures) as well as a check for significant trending over the range of the measurements. If the bias is significant then the results of the two differ by an overall offset in their measurements. If the trending (slope of the regression line) is significant then the difference between the two measurements changes as their magnitude changes which means the two methods are not in agreement.

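### The single regression slope can miss a patch that follows a patient's own temperature changes poorly, and the tests on the mean difference cannot be relied on to catch it

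*Combined protocol and SAP*

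**What the plan says.** The Purpose is to "assess the accuracy and precision of the Temp-Traq thermometer for monitoring body temperature in adult patients under three conditions", and the Design section describes a repeated-measures, within-group comparison. Procedure and Analysis schedule a baseline pair of readings and three more at two-hour intervals: "This will provide 4 repeated temperature measures per patient".

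The Analysis section plans three checks on these data.

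- **Equivalence of means.** "We will use the TOST (Two One Sided t-tests) method for equivalence testing", with the criterion that the mean "measurements of the two methods should be within ± 0.2 degrees of each other".
- **Bias.** Under agreement testing, a significance test of the average difference.
- **Trend.** Also under agreement testing: "If the trending (slope of the regression line) is significant then the difference between the two measurements changes as their magnitude changes". A significant slope is read as lack of agreement.

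The section does not say whether the line is fitted to all 160 pairs or to 40 patient means. It does not say whether the horizontal axis is the pair average or the PA reading, what significance level applies, or how repeated readings on one patient are handled. Nothing separates differences between patients from change within a patient.

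**The concern.** A monitoring device has to show a patient's own rise or fall. Four readings over six hours can give information on that, but no planned analysis isolates it.

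TOST and the bias check use the mean difference. If a patch shows only half of each departure from the patient's own average, the shortfalls on rises and falls cancel and the mean difference stays near zero. The single slope is spread over the whole temperature range, most of which may come from patients differing from one another, so damping within patients is diluted. Stable patient-specific offsets of the patch also push the slope the other way and can cancel it.

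The trial could then report equivalent means and no significant trend for a patch that shows about half of each patient's temperature change.

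**Working it through.** **1. The plan's own figure.** The plan gives power for TOST only. With the .032 SD taken ten-fold and correlation .7, the SD of a paired difference is .32 × √(2 × (1 − .7)) = .248. With 40 patients, margin ±.2 and an assumed level of .05 per side (t, 39 df), power is 80.6% at a true difference of .1, which agrees with "A sample size of 40 patients will provide 80% or greater power for testing for equivalence between methods". At .15 it is 34.8%, which agrees with "where the difference is .15 and the standard deviation is a ten-fold increase, is 35" per cent. So the TOST power reproduces. The plan states no operating characteristics for the slope check.

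**2. Model and inputs.** From the plan: 40 patients, 4 readings, margin ±.2. Assumed, because the plan gives none of them: between-patient SD B = .7, within-patient SD W = .3, patient-specific patch offset SD S = .2 (also 0), and reading noise N = .05 on each device. PA = patient mean + change + noise. Patch = patient mean + g × change + offset + noise, with g = 1 (full follower) or g = .5 (half-follower). Changes are independent around the patient's own mean.

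**3. Mean difference.** Its expectation is (g − 1) × (average change) = 0 for either g. TOST passes both patches in essentially every simulated trial at these values.

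**4. Pooled slope of difference on pair average.**

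Numerator: −(1 − g)(1 + g)/2 × W² + S²/2

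Denominator: B² + ((1 + g)/2)² × W² + S²/4 + N²/2

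- Half-follower, S = .2: (−.375 × .09 + .02) / (.49 + .0506 + .01 + .00125) = −.01375/.5519 = −.025
- Full follower, S = .2: .02/(.49 + .09 + .01 + .00125) = .02/.5913 = +.034
- Half-follower, S = 0: −.03375/(.49 + .0506 + .00125) = −.03375/.5419 = −.062
- Full follower, S = 0: 0

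With offsets, the half-follower's expected slope is closer to zero than the full follower's.

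**5. Within-patient slope of patch on PA.** This is g × W²/(W² + N²). For g = 1 it is .09/.0925 = .97, and for g = .5 it is .49. Offsets and between-patient spread drop out.

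**6. Simulated pass rates** (TOST passed and slope not significant at two-sided .05; B = .7, N = .05):

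| Setting | Slope fitted to | Half-follower | Full follower |
|---|---|---|---|
| W .3, S .2 | 160 pairs | 68% | 57% |
| W .3, S .2 | 40 patient means | 93% | 87% |
| W .3, S 0 | 160 pairs | 5% | 95% |
| W .3, S 0 | 40 patient means | 83% | 94% |
| W .4, S .2 | 160 pairs | 38% | 58% |

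Repeat runs moved these by up to a few points without changing the pattern. Adding the bias check in the first row gave 64% against 53% in one such run.

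**7. Without offsets but with larger noise.** At S = 0, W = .2 and difference noise at the ten-fold .248, the pooled line passes the half-follower 83% of the time, against 95% for the full follower. The miss therefore does not rest on offsets alone.

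**8. Limit of the within-patient slope.** PA noise attenuates it. At W = .2 and N = .10 a full follower averages .04/(.04 + .01) = .80.

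**The case against.** The strongest reply is that the result depends on the inputs and on the failure chosen.

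- **No SDs in the plan.** It ties the ASTM figures to within-patient variation and gives no patient-offset SD. With no offsets and low noise, the pooled slope rejects the half-follower 95% of the time. This stands, and it is why no general miss rate can be claimed.
- **A selective failure.** The simulated patch gets each patient's mean right and damps only departures from it. If damping also applied between patients, the slope would detect it: in simulation neither the pooled nor the patient-means slope let such a patch through. If patients drift in one direction and the patch lags from baseline, the mean difference shifts and TOST could detect it. Lag was not simulated. These limits stand.
- **Scope.** This is a feasibility study whose aims are accuracy, precision and consistency across three conditions. Following is not a named aim. That is fair, but the title and Purpose are about monitoring, and repeated readings are built into the design.

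Two stronger readings are tempting. A reader might infer that the planned tests pass a half-following patch as often as a perfect one. The documents do not support that: a patch with no offsets passes about 95% of the time, and at within-patient SD .4 with offset .2 the pooled line passes the half-follower less often (38% against 58%). Nor does the plan state that the line runs over all readings.

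A reader might also turn the ±.2 margin into a rule that the slope's lower limit exceed .8. That margin is a mean difference in degrees, not a loss per degree. At within-patient SD .2 and noise .10, a perfect follower would meet such a rule only about 3% of the time.

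**Conclusion.** The point holds in a limited form. No planned analysis isolates whether the patch follows a patient's own change. The single slope can miss poor following, and the two tests on the mean difference are blind to it when changes centre on each patient's mean.

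The size runs from a serious miss to almost none, depending on within-patient SD, patient offsets, noise, and whether pairs or patient means are used. All of these are unstated. Patient means perform poorly in both settings tabulated; the pooled line works when offsets are absent and within-patient change is large relative to noise. The within-patient slope separates the two patches in the central case (.49 against .97), provided temperatures move enough relative to PA noise. This is a worthwhile, inexpensive improvement and does not invalidate the TOST.

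**What to change.** In the agreement-testing paragraph of Analysis, replace the single slope by a regression of the patch reading on two terms: the patient's mean PA temperature, and each PA reading's deviation from that mean. Report the second as patch change per 1 degree of PA change, with a 95% CI clustered by patient. State that agreement for monitoring will not be claimed from a pooled slope alone. TOST and the bias check can stay as they are.

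Read the within-patient slope descriptively, without a fixed cut-off. Report the within-patient SD of the PA readings beside it, and show how far plausible PA noise alone would pull a perfect follower below 1 (for example to .97 or .80, as worked above). If temperatures barely move within patients, report following as not assessable.

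The cost is one extra regression and a few sentences of text, with no new patients or readings. The downside is an attenuated or uninformative result when within-patient change is small relative to PA noise.
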